
Role of this analysis plan

To better understand the mechanism of action of TMS, and of any putative benefit of cgitBS over standard repetitive TMS, we will examine a set of hypotheses derived from prior literature. Here, we describe the spectroscopic processing and statistical analysis plan.

The main study rationale is to assess whether clinical response to treatment is associated with GABA changes in the DLPFC.

Definitions of measures

- *Clinical improvement*
Mean change in depression measure from baseline (17-item HDRS total score as primary measure); changes from baseline in BDI, QIDS-SR-16, PHQ-9 and GAD-7 will be used for exploratory analyses only)
- *Treatment response*
Reduction in depression measure (17-item HDRS total score) of 50% or greater compared to baseline
- *Metabolite ratios*

GABA levels relative to Cr (GABA+/Cr), Glx levels relative to Cr (Glx/Cr) and GABA levels relative to Glx (GABA+/Glx as no macromolecule suppression). Glx and Cr will be estimated from non-edited spectra.

Primary hypotheses

1. Changes in depression symptoms on 17-item HDRS (16 weeks versus baseline) will be associated with change in GABA+/Cr between baseline and 16 weeks (post minus pre-treatment) in both treatment groups with increase in GABA+/Cr expected to be associated with decrease of HDRS (improvement).
2. Changes in depression symptoms on 17-item HDRS (26 weeks versus baseline) will be associated with change in GABA+/Cr between baseline and 16 weeks (post minus pre-treatment) in both treatment groups with increase in GABA+/Cr expected to be associated with decrease of HDRS (improvement).
3. Greater clinical improvement on 17-item HDRS (16 and 26-week vs baseline) will be associated with lower GABA+/Cr at baseline across both treatment groups.

Secondary hypotheses

1. GABA+/Cr will be increased after treatment compared to baseline for treatment responders across both treatment groups (a) and (b) GABA+/Cr increase will be higher in responders than in non-responders.
2. GABA+/Cr increase will be higher in cgtTBS compared to rTMS group (all patients).
3. Greater averaged and sustained clinical improvement on 17-item HDRS (averaged over 8,16 26-week follow-up) will be associated with more GABA+/Cr change across both treatment groups.
4. Greater averaged and sustained clinical improvement on 17-item HDRS (averaged over 8, 16 26-week follow-up) will be associated with lower GABA+/Cr at baseline across both treatment groups.

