- 16-item self-report Quick Inventory of Depression Symptoms (QIDS-SR-16) at baseline, 8-week follow-up, 16-week follow-up and 26-week follow-up
- 9-item Personal Health Questionnaire (PHQ-9) at baseline, 8-week follow-up, 16-week follow-up and 26-week follow-up
- Total score on the GAD-7 measure of anxiety
- Massachusetts Treatment Resistance category (mild, moderate, severe as defined in trial protocol)

Regions of interest (ROIs) / Voxel of interest (VOI)

- For MRS, a voxel (20x45x30mm) was placed on the left DLPFC based on the individual T1 anatomical image acquired prior to the MRS session.
- Grey Matter (GM), White Matter (WM) and Cerebrospinal fluid (CSF) will be parcellated through GANNET segmentation with SPM12. The GM values will be covariates of no interest in the statistical analysis.

Sensitivity analyses

In order to examine whether quality of MRS affected the results, we will conduct sensitivity analyses to

- assess a potential effect from outliers in voxel position. For this, coverage of anatomical DLPFC (in percent) and overlap with TMS brain target within the individual MRS voxels will inform through the sensitivity analysis.
- assess spectral fitting quality effects. For this, only data with higher quality data fit will be used to repeat primary and secondary hypothesis with $p < 0.1$ results.

Statistical tests

Primary Hypotheses

- The correlation between change in GABA+/Cr between baseline and 16 weeks (post minus pre-treatment) and clinical improvement will be tested by regression with the following covariates for P1 and P2:
 - *Age*
 - *Sex*
 - *Treatment group (rTMS or cgtTMS)*
 - *MGH treatment resistance*
 - *Baseline 17-item HDRS*
 - *Study centre*
 - *MRS platform (scanner/protocol)*
 - *MRS quality (GABA+ fitting error)*

$P < 0.01666$ will be the level considered for statistical significance ($p < 0.05/3$, i.e. 5% significance level with Bonferroni correction for 3 co-primary hypotheses). For missing data (e.g. due to poor spectra quality, participants' absence for the scanning or incompleteness of whole MRS sessions) we will take an available data approach, meaning individuals with enough data for a model will be included in that model's analysis.

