- For P3, a mixed effects model will be used with participant as random effect to account for three repeated measures. Each participant will contribute up to 3 repeated outcome measures to the model in addition to the baseline HDRS-17 score. The model will be adjusted for the stratification and minimisation variables: baseline HDRS-17 score, baseline Massachusetts General Hospital Treatment Resistant Depression score, and study centre as part of the covariable detailed above. For missing data, we will take an available data approach, meaning individuals with enough data for a model will be included that model's analysis.

Secondary Hypotheses

Secondary hypotheses S2, S3, S5, S6, S7 will be analysed as above, for S1 and S4 we will use a mixed model

- A Linear mixed model will be used with GABA+/Cr as the dependent variables.
- Independent variables will be the *Treatment* response group, *Time* (pre-and post) and *Treatment type*
- Covariates of no interest include
 - *Age*
 - *Sex*
 - *MGH treatment resistance group*
 - *Study centre*
 - *MRS platform (scanner/protocol)*
 - *MRS quality (GABA+/Glx fitting error respectively)*

We will take an available data approach, meaning individuals with enough data for a model will be included in that model's analysis. For secondary analyses $P < 0.05$ will be considered significant without Bonferroni correction.

The statistical analysis for primary and secondary hypotheses will be performed using a current version of either SPSS, SAS, Stata or R (for graphical illustrations). Diagnostic plots of model residuals, and the results of the Shapiro-Wilk test, will be used to determine whether variable transformations are required.

Exploratory hypotheses

Exploratory tests will be undertaken using current versions of either established advanced image analyses, SPSS, SAS, Stata or R (for graphical illustrations).

Included participants

All trial participants with baseline T1-weighted structural MRI, and MRS passing quality control criteria as detailed later in this document. We will include only participants that received the treatment to which they were assigned (that is, participants without protocol deviations on the basis of stimulation sequence or localisation method used).

Data processing

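### In the S1 mixed model, age, sex, MGH group, centre and platform have no Time interaction, so they cancel from the pre/post change and do not adjust the responder comparison in S1(b)

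*SAP*

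**What the plan says.** Under Secondary hypotheses, S1(b) states that "GABA+/Cr increase will be higher in responders than in non-responders". Under Statistical tests, Secondary Hypotheses, the SAP says that "for S1 and S4 we will use a mixed model", and then: "A Linear mixed model will be used with GABA+/Cr as the dependent variables". So the outcome is the level at each scan, not the change. The factors are given as "Independent variables will be the *Treatment* response group, *Time* (pre-and post) and *Treatment type". A second list, introduced by "Covariates of no interest include", holds age, sex, MGH treatment resistance group, study centre, MRS platform and MRS quality (fit error). No interaction is written for any term in either list.

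The section on regions of interest adds that grey matter values will be covariates of no interest in the analysis generally.

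For the primary hypotheses, the association between change in GABA+/Cr and clinical improvement "will be tested by regression with the following covariates for P1 and P2". That list includes treatment group, MGH resistance, centre, platform, age and sex.

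**The concern.** S1(b) is about a difference in within-person change. In a model of levels at two times, that difference is the Response x Time coefficient. A covariate that is constant within a person and has no Time interaction shifts both scans equally, so it cannot affect that coefficient. An analyst who adds the missing Response x Time term and otherwise follows the covariate list would report S1(b) as adjusted for centre and platform when it is not.

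Platform matters most. Under Data processing the SAP describes three scanner/site combinations (Nottingham GE, Nottingham Philips, Newcastle Philips). If measured GABA+/Cr drifts differently on these platforms and response rates also differ between them, responders and non-responders will differ in GABA change with no link between response and GABA on any one platform. P1 and P2 address nearly the same question with these factors adjusted on the change, so the two routes are not adjusted alike.

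**Working it through.** **No figure to reproduce.** The SAP gives no sample size, SD, effect size or response rate for S1. All sizes below are assumptions.

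**Algebra.** Let R be response group, t = 0 or 1 for the two scans, x the person-level covariates and q the scan-level ones:

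y(i,t) = b(i) + β_R R(i) + β_T t + γ R(i) t + θ x(i) + φ q(i,t) + e(i,t)

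Subtracting the first scan from the second:

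y(i,1) − y(i,0) = β_T + γ R(i) + φ [q(i,1) − q(i,0)] + [e(i,1) − e(i,0)]

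The term θ x(i) is gone, so γ (the S1(b) contrast) is not adjusted for x. It would be adjusted if the model also held λ x(i) t. Fit error, and grey matter from the MRS voxel, belong to q and do not cancel.

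**Numerical check.** Random-intercept REML fits to simulated data, N=100, Response x Time estimate (SE):

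| Model | Complete pairs | 20% of week-16 scans missing | 35% missing |
|---|---|---|---|
| No covariates | 0.2439 (0.2249) | −0.0679 | −0.2239 |
| Arm, age, sex, MGH, platform as level terms | 0.2439 (0.2249) | −0.0676 | −0.2185 |
| Level terms plus fit error | 0.2384 (0.2244) | −0.0569 | −0.2318 |
| Level terms plus arm x Time | 0.1499 (0.2237) | −0.1448 | −0.2612 |
| All person-level terms x Time | 0.2951 (0.2454) | −0.1973 | −0.2336 |

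Each column is one simulated data set. With complete pairs, 0.2439 is also the raw difference in mean change. Level terms leave it unchanged, and almost unchanged when scans are missing. By-Time terms move it.

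**Size by arm.** Assume equal arms, SD of change 1, response 30% and 50%, an arm difference in change of 0.5 SD, and no response effect within either arm.

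- Share of responders in the second arm: 0.50/(0.30 + 0.50) = 0.625.
- Share of non-responders in that arm: 0.50/(0.70 + 0.50) = 0.417.
- Expected difference in change: 0.5 × (0.625 − 0.417) = 0.104 SD.
- Group SD, including the arm difference: about √(1 + 0.25 × 0.24) = 1.03.
- N=100 (40 responders, 60 not): SE = 1.03 × √(1/40 + 1/60) = 0.210. The ratio is 0.104/0.210 = 0.50, and two-sided rejection at 5% is about 7.9%.
- N=200 (80 and 120): SE = 1.03 × √(1/80 + 1/120) = 0.149. The ratio is 0.70, and rejection is about 10.8%.

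Two separate simulations (4,000 and 5,000 runs per setting) gave 7.8% and 7.5% at N=100, and 11.1% and 10.5% at N=200. Other settings, with 5,000 runs each:

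| Setting | N=60 | N=100 | N=200 |
|---|---|---|---|
| Arm 0.5 SD, response 40/40% | 4.9% | 4.9% | 5.5% |
| Arm 0.5 SD, response 35/45% | 5.3% | 5.7% | 7.0% |
| Arm 0.5 SD, response 30/50% | 6.4% | 7.5% | 10.5% |
| Arm 0.5 SD, response 25/55% | 8.6% | 11.1% | 18.7% |
| Three platforms, 0.5 SD per step, equal response | 5.1% | 5.0% | 5.5% |
| Three platforms, 0.5 SD and 10 points of response per step | 7.4% | 9.5% | 14.2% |

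With arm on the change, the arm settings return to 4.5–5.5%. With platform on the change as well, the platform settings return to 4.7–5.1%.

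**The case against.** **Arm.** A reader might infer that treatment type, too, is only a level effect and that S1(b) is wholly unadjusted. The SAP does not support this. It writes no interactions at all. Read literally, even response group is level-only and S1(b) is not tested. Treatment type stands beside Time and response group, apart from the nuisance covariates, so a factorial reading that includes Treatment type x Time is open. That reading would not help age, sex, MGH group, centre or platform. Nor is S1(b) wholly unadjusted, because fit error and grey matter can differ between scans.

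**Which null.** S1 is worded across both treatment groups. On a marginal reading, the 0.104 SD difference in the arm example is real and rejecting is correct. The arm figures are false-positive rates only if a within-arm association is intended, which S1 does not say. This objection stands for arm. It is weaker for platform, where a drift in measurement is plainly nuisance.

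**Size.** A difference in GABA change by arm or platform is not enough, because response must differ by the same factor. Larger figures can be produced: 29.5% at N=100, with 0.8 SD differences by both arm and platform and 20-point response gaps by both. Nothing in the SAP supports such sizes, and its Introduction reports no GABA change at 3 months in the pilot.

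**S5(b).** The SAP sends S5 to the methods given above for the primary hypotheses. The mention of Glx fit error in the covariate list hints that this model may also serve Glx, but does not establish it.

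**Importance.** P1 and P2 carry the GABA question with adjustment and a corrected significance level. This stands and limits the weight of the point.

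**Conclusion.** The cancellation is algebra and holds whatever the data: as listed, age, sex, MGH group, centre and platform do not adjust S1(b), exactly with complete pairs and almost exactly with missing scans. This goes beyond missing detail, because adding the obvious Response x Time term leaves it in place. For treatment type the SAP is unclear rather than wrong.

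The consequence is conditional. S1(b) can reject without a response–GABA link inside platforms or centres (or inside arms, if a within-arm association is meant) only when GABA change and response rate both differ by that factor. Under the assumed 0.5 SD and 20-point gaps by arm, rejection is roughly 7.5–8% at N=100 and 10.5–11% at N=200 against a nominal 5%. With equal response rates it is about 5%. Minor to moderate: S1 is secondary, though tested at an uncorrected 0.05 and close to the stated main rationale.

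**What to change.** Write out the S1 fixed effects: Response x Time, Treatment type x Time, centre/platform x Time and MGH group x Time, with age x Time and sex x Time if adjustment for those is intended. Take S1(b) from the Response x Time coefficient. State whether a within-arm or a marginal association is meant. If study centre means scanning site, platform already determines it and one platform x Time term is enough.

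Alternatively, regress the change in GABA+/Cr on response group with the P1/P2 covariates. For complete pairs and the same person-level covariates, the two forms give the same adjustment. Regressing the week-16 level on response and baseline level would target a different quantity from the difference in increase that S1(b) names.

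The cost is wording and a few degrees of freedom. With three platforms and three MGH categories, the by-Time terms beyond Response x Time take 1 + 2 + 2 = 5, or 7 with age and sex, if platform determines centre. The change-score form uses only participants with both scans, whereas the mixed model keeps the available-data approach. Apply the same change to S5(b) only if it is run with this model.

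### The S1 mixed model leaves out baseline HDRS-17, so the S1(b) responder comparison of GABA+/Cr change can be confounded by baseline severity

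*SAP*

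**What the plan says.** **Responder definition** (SAP, Definitions of measures): "Reduction in depression measure (17-item HDRS total score) of 50% or greater compared to baseline". Baseline HDRS-17 is the denominator.

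**Hypothesis S1(b)** (SAP, Secondary hypotheses): "GABA+/Cr increase will be higher in responders than in non-responders". S1(a) concerns the increase within responders only.

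**Primary models** (SAP, Statistical tests). The covariate list for P1 and P2 contains "Baseline 17-item HDRS". For P3 the text reads: "The model will be adjusted for the stratification and minimisation variables: baseline HDRS-17 score", followed by the MGH score and study centre.

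**S1 model** (SAP, Statistical tests, Secondary Hypotheses). The dependent variable is the GABA+/Cr level. The independent variables are response group, time and treatment type, and no interaction is written out. The list headed "Covariates of no interest include" has age, sex, MGH group, study centre, MRS platform and MRS quality.

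**Allocation of hypotheses to models:** "Secondary hypotheses S2, S3, S5, S6, S7 will be analysed as above, for S1 and S4 we will use a mixed model".

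**The concern.** Of the three stratification and minimisation variables named for P3, two (MGH and centre) are carried into the S1 list. Baseline HDRS-17 is dropped, and no reason is given.

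Responders and non-responders are not randomised groups. They are formed by comparing follow-up HDRS-17 with half of baseline HDRS-17, so baseline severity can enter the grouping variable directly. If GABA+/Cr change also varies with baseline severity, S1(b) attributes to response a difference that belongs to severity. P1, which relates the same GABA+/Cr change to continuous HDRS-17 change, controls for this; S1(b) does not.

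At stake is the interpretation of one secondary mechanistic comparison, tested at an uncorrected 0.05.

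**Working it through.** The SAP states no sample size, power or effect size for S1, so there is no figure of its own to reproduce.

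**1. The covariate lists side by side**

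| Variable | P1/P2 | P3 | S1 model |
|---|---|---|---|
| MGH resistance | yes | yes | yes |
| Study centre | yes | yes | yes |
| Baseline HDRS-17 | yes | yes | no |

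**2. When does response depend on baseline severity?** Write follow-up F = a + s(B - 23) + e, with baseline B. A participant responds if F <= 0.5B, that is if a - 23s + (s - 0.5)B + e <= 0. The dependence on B therefore has the sign of (s - 0.5). If s is above 0.5, milder patients respond more often; at 0.5 there is no gradient; below 0.5 it reverses.

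**3. Size under assumed inputs.** None of these comes from the SAP: B normal with mean 23 and SD 4, entry at 16 or more; residual SD 6.5; a set so that one third respond (p = 1/3); two-sided 5% test; n = 80 or 120; no true effect of response on GABA+/Cr change.

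Let gap be the difference in mean B between responders and non-responders, in SD units. Let r be the correlation of baseline HDRS-17 with GABA+/Cr change. The spurious standardised difference is d = r x gap, the non-centrality is k = |d| x sqrt(n p (1 - p)), and the size is Phi(-1.96 + k) + Phi(-1.96 - k).

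| Slope s | Response, B < 20 | Response, B > 26 | Gap (SD) | Size at r = 0.3, n = 80 / 120 | Size at r = 0.4, n = 80 / 120 |
|---|---|---|---|---|---|
| 1.0 | 47% | 21% | -0.435 | 8.5% / 10.3% | 11.4% / 14.6% |
| 0.7 | 39% | 28% | -0.180 | 5.6% / 5.9% | 6.1% / 6.6% |
| 0.5 | 33% | 33% | 0.00 | 5.0% / 5.0% | 5.0% / 5.0% |
| 0.3 | 28% | 39% | 0.186 | 5.6% / 6.0% | 6.1% / 6.7% |

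Worked example (s = 1, r = 0.4, n = 80): |d| = 0.4 x 0.435 = 0.174. Then k = 0.174 x sqrt(80 x 2/9) = 0.174 x 4.216 = 0.734. The size is Phi(-1.226) + Phi(-2.694) = 0.110 + 0.004 = 0.114.

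At r = 0.2 the size is at most 7.3%, even with s = 1 and n = 120.

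**4. Would listing baseline HDRS-17 be enough?** The outcome is GABA+/Cr at two times. For a complete pair, a covariate H that is fixed for the person and enters as a level adds the same amount at both times, so it cancels from the post-minus-pre difference. Only H x Time adjusts that difference.

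A simulation of a random-intercept model confirms this. The assumptions were n = 120, about one third responders, random-intercept SD 1, residual SD 0.7, log-odds of response -0.5 per SD of severity, GABA change +0.3 per SD, and 300 runs with complete pairs:

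| Adjustment for baseline HDRS-17 | Mean Response x Time estimate (truth 0) | Rejection rate |
|---|---|---|
| None | -0.164 | 14.0% |
| Main effect only | -0.164 | 14.0% |
| With H x Time | -0.017 | 4.7% |

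With 20% of follow-up scans missing, no adjustment and main effect only still agreed closely (mean -0.128 and -0.127). When either link was set to zero, the mean estimate stayed between -0.013 and -0.003.

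**The case against.** The strongest objection is that the missing list entry is not the working defect. Printed beside the other covariates as a level, baseline HDRS-17 would leave S1(b) unchanged when pairs are complete. The deeper gap is that the SAP writes no interaction terms for this model. This stands, and it determines the form of the fix.

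The comparison with the primary models can also be questioned. In P3 the outcome is HDRS-17, and P1 and P2 concern HDRS-17 change, so baseline HDRS-17 belongs there as the baseline of the clinical measure. In S1 the dependent variable is GABA+/Cr. Minimisation status, for its part, supports adjusting the randomised arm comparison, not a comparison of responders. Both remarks are fair. The reason to adjust S1(b) is that response is defined relative to baseline severity and that P1, its continuous counterpart, is adjusted.

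The list may not be complete: its heading says include, and the Regions of interest section makes grey matter a covariate although neither list prints it. That is a further reason to give one full list, but it does not show that baseline HDRS-17 was intended.

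A reader might infer several stronger things that the SAP does not support:
- **That response must depend on baseline severity.** It need not. The gradient vanishes at slope 0.5 and reverses at 0.3.
- **That S1(a) is biased in the same way.** It is a change within responders, with no group comparison to confound.
- **That S5(b) has the same fault.** The SAP sends S5 to the methods stated above, where baseline HDRS-17 is a covariate. The mention of a Glx fitting error in the S1 list suggests S5 may have been meant for the mixed model, but the text does not say so.
- **That any disagreement between S1 and P1 would come from the adjustment sets alone.** The two also differ in dichotomised against continuous improvement, in model type and in significance level (0.05 against 0.01666).

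**Conclusion.** The point holds for S1(b). The model omits a variable that the three primary analyses adjust for and against which response is defined, so the responder comparison is open to confounding by baseline severity.

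Bias requires severity to relate to both response and GABA+/Cr change. The SAP gives no figure for either link, so the direction is unknown and the bias may be nil. Under the assumptions shown, the nominal 5% test has a true size of about 5-7% at slopes of 0.3 to 0.7. The 11-15% figure needs slope 1 and a correlation of 0.4 together, and should not be read as the expected error rate.

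Severity is minor to moderate: one part of one secondary hypothesis is affected, and no primary analysis.

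**What to change.** For S1(b), write the Response x Time term into the model as the tested contrast, and add baseline HDRS-17 together with baseline HDRS-17 x Time. With complete pairs, an equivalent form is to regress GABA+/Cr change on response group with baseline HDRS-17 as a covariate.

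In the same edit, give one complete covariate list for this model, and reconcile which secondary hypotheses use it. S5 is worded like S1 but sent elsewhere. S4 relates averaged HDRS-17 improvement to baseline GABA+/Cr, which does not fit a model of GABA+/Cr by response and time. If S5(b) is moved into this model, the same two terms apply to it.

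The cost is a short SAP amendment and about two degrees of freedom. Baseline HDRS-17 is already in the Required data list, so nothing new has to be collected.
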